## 12.2. Safety Analyses

### 12.2.1. Analysis Plan

The analysis will be done on the intent to treat population and patients who drop out will be censored at the point of last follow up.

The primary endpoint of the study is 6-month Progression-free survival (PFS), which is defined as number of days from the first day of taking study dose to the earlier of death or disease progression by RECIST v1.1 for solid tumors. Median PFS will be estimated using the Kaplan-Meier method.

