#### 4.12. Subject Withdrawal/Discontinuation Criteria

Subjects may withdraw consent at any time for any reason or be dropped from the study at the discretion of the investigator should any untoward effect occur. In addition, a subject may be withdrawn by the investigator or the Sponsor if enrollment into the study is inappropriate, the study plan is violated, or for administrative and/or other safety reasons.

A subject must be discontinued from the study for any of the following reasons:

- The subject or legal representative (such as a parent or legal guardian) withdraws consent.
- Confirmed radiographic disease progression
  - Note:* For unconfirmed radiographic disease progression, please see Section 10.
  - Note:* A subject may be granted an exception to continue on treatment with confirmed radiographic progression if clinically stable or clinically improved
- Unacceptable adverse experiences
- Intercurrent illness that prevents further administration of treatment
- Investigator's decision to withdraw the subject
- The subject has a confirmed positive serum pregnancy test
- The subject is lost to follow-up
- Completed 24 months of uninterrupted treatment with pembrolizumab or 35 administrations of study medication, whichever is later.

*Note:* 24 months of study medication is calculated from the date of first dose. Subjects

who stop pembrolizumab after 24 months may be eligible for up to one year of additional study treatment if they progress after stopping study treatment provided they meet the requirements detailed in Section 4.8.

- Administrative reasons

The EOT and Follow-up visit procedures are listed in Section 9 (Study Calendar) and Section 4 (Visit Requirements). After the end of treatment, each subject will be followed up to 30 days or until new anti-cancer treatment is initiated, whichever occurs first for adverse event monitoring, including SAEs. Subjects who discontinue for reasons other than progressive disease will have post-treatment follow-up for disease status until disease progression, initiating a non-study cancer treatment, withdrawing consent or becoming lost to follow-up. After documented disease progression each subject will be followed by telephone for overall survival until death, withdrawal of consent, or the end of the study, whichever occurs first.

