**Table 8: Response Evaluations based on Endpoints**

	Progression Free Survival (PFS)	Response Rate (RR)	Overall Survival (OS)	Safety
Primary or Secondary	Primary	Secondary	Secondary	Secondary
Definition and Time Frame	Time from first treatment to documented disease progression or death due to any cause	Defined as proportion of patients with RECIST v1.1 response (sum of partial and complete responses).	Time from first treatment until the day of death due to any cause	Assessed on the basis of adverse events (AEs; graded according to the National Cancer Institute Common Terminology Criteria for Adverse Events, version 4.03)
Safety Issue (Yes/No)	No	No	No	Yes
Relevant Subset	Patients who receive baseline imaging and at least first follow-up imaging at 9 weeks.	Patients who receive baseline imaging and at least first follow-up imaging at 9 weeks.	All enrolled patients	Patients who receive at least 1 dose of pembrolizumab.
Measurement Method	CT or MRI every 9 weeks	CT or MRI every 9 weeks	CT or MRI every 9 weeks	CTCAE v5
Measurement Time Points	Every 9 weeks	Every 9 weeks	Every 9 weeks	Day 1 of each cycle

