## 12. STATISTICS CONSIDERATIONS

### 12.1. Statistical Design

This is a single-stage study for the doublet epacadostat and pembrolizumab. A 6-month PFS of 20% was observed using single agent pembrolizumab and is the basis for the null hypothesis of the present study (Bang, abstract 4001, GI ASCO 2015). We will enroll 30 patients over 18 months and follow patients for at least 6 months. This design has 80% power to reject a 20% PFS rate, if the true PFS is 39%. Calculation based on binomial probabilities with a one-sided significance of 10%. The level of significance for the primary endpoint in Phase 2 is one-sided 10%, which is deemed acceptable for a proof-of-concept study.

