### 12.3. Secondary Analyses

Secondary efficacy analysis will be conducted for the efficacy evaluable population. Secondary endpoints and analyses are as follows:

To evaluate response rate (RR). Response will be determined by RECIST v1.1 for solid tumors. The 95% exact CI for the RR will be estimated using the Clopper-Pearson method. For objective responders, the duration of response is the time from the first objective response contributing to an objective response, to the first objective response of PD (by RECIST v1.1) occurring after the first objective response contributing to the objective response.

To evaluate overall survival (OS). Time-to-event data will be analyzed by the Kaplan-Meier method, treating subjects with no observed death or progression as censored at their last date known to be alive. For the OS analysis, the nonparametric Kaplan-Meier method will be used to estimate the survival time distribution and the median survival.

To assess the safety and tolerability of epacadostat in combination with pembrolizumab. AEs will be coded by the MedDRA, and incidences will be tabulated by preferred term and system organ class for all events, related events, and events  $\geq$  Grade 3. Severity of AEs will be based on the CTCAE v5 scale as indicated. Quantitative safety variables and their changes from baseline (laboratory, vital signs) will be summarized with descriptive statistics. Clinically significant abnormal values will be flagged and tabulated based on predefined criteria. Exposure will be analyzed by describing dose intensity, which is defined as the dose-received divided by the dose planned over a given time interval. This will be done by cycle as well as overall cycles received for epacadostat and pembrolizumab. For each cycle, incidences of dose reductions and cycle

delays will also be tabulated, by reason for the reduction or delay. The percentage of subjects with any delay and/or reduction will also be calculated.

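### Section 12.2.1 does not carry the 12.1 test of 6-month PFS against 20% into the primary analysis, and Table 8 restricts PFS to a subset that conflicts with intent-to-treat

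*Combined protocol and SAP*

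**What the plan says.** **Design.** Section 12.1, repeated in the synopsis, takes a 6-month PFS of 20% as the null and enrols 30 patients. It states: "This design has 80% power to reject a 20% PFS rate, if the true PFS is 39" per cent, and "Calculation based on binomial probabilities with a one-sided significance of 10" per cent. It attaches the one-sided 10% level to the primary endpoint. No rejection count is given. Section 12.5, where a success criterion could stand, contains only template instructions.

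**Analysis.** Section 12.2.1 (under the heading for safety analyses) names 6-month PFS as primary but defines it as a number of days to death or RECIST progression. The one method it gives is "Median PFS will be estimated using the Kaplan-Meier method". There is no 6-month estimate, interval, test or rule for patients whose 6-month status is unknown.

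**Population.** Section 12.2.1 uses the "intent to treat population and patients who drop out will be censored at the point of last follow up". In section 10.4, Table 8 gives the relevant subset for PFS as "Patients who receive baseline imaging and at least first follow-up imaging at 9 weeks", while defining PFS as "Time from first treatment to documented disease progression or death due to any cause".

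**Censoring.** The last follow-up in 12.2.1 is not defined. Section 4.12 provides "post-treatment follow-up for disease status until disease progression, initiating a non-study cancer treatment", and sections 4.6.2 and 4.9.2 also end imaging at new therapy. Telephone survival contact continues after that (4.6.3). The overall survival item in 12.3 speaks of "treating subjects with no observed death or progression as censored at their last date known to be alive".

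**The concern.** The trial is open-label with a single arm and one primary decision. As written, two analysts following the document could use different populations, different censoring dates and different summaries, and reach different conclusions from the same data. A Kaplan-Meier median cannot reject or retain a 6-month rate of 20%.

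The Table 8 restriction has a direction. Patients without a 9-week scan are likely to be mainly those who died or deteriorated early. Removing failures raises the observed PFS rate, in favour of the treatment. It also puts Table 8 at odds with itself, since a death at week 5 is an event by its definition but the patient is outside its subset.

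**Working it through.** **1. Reproduce the design.** Inputs from 12.1: n=30, null 0.20, alternative 0.39, one-sided level 0.10, exact binomial.

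- P(Bin(30, 0.20) ≥ 9) = 0.1287, above 0.10.
- P(Bin(30, 0.20) ≥ 10) = 0.0611, so the rule is to reject at 10 or more of 30.
- P(Bin(30, 0.39) ≥ 10) = 0.7934, which matches the stated 80%.

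The exact one-sided 90% lower bound agrees with this rule: 21.8% at 10/30 and 19.0% at 9/30.

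**2. Can the population change the decision?** Take 9 patients progression-free at 6 months and 2 of the failures without a 9-week scan.

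- Intent-to-treat: 9/30, p = P(Bin(30, 0.20) ≥ 9) = 0.129, do not reject.
- Table 8 subset: 9/28, p = P(Bin(28, 0.20) ≥ 9) = 0.090, reject.

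**3. Type I error under Table 8.** Let the all-patient rate be 20% (an expected 6 of 30), and let m patients, all early failures, be dropped. The subset has n = 30 − m and rate 6/n. The re-derived cutoff c is the smallest with P(Bin(n, 0.20) ≥ c) ≤ 0.10.

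| m | n | subset rate | c | type I error, cutoff c | type I error, cutoff kept at 10 |
|---|---|---|---|---|---|
| 1 | 29 | 20.7% | 10 | 6.0% | 6.0% |
| 2 | 28 | 21.4% | 9 | 12.7% | 5.9% |
| 3 | 27 | 22.2% | 9 | 12.6% | 5.8% |
| 4 | 26 | 23.1% | 9 | 12.4% | 5.7% |
| 5 | 25 | 24.0% | 9 | 12.3% | 5.6% |

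**4. How many might be dropped?** The documents do not say. As an illustration, section 2.1 reports 6-month overall survival of 66% and median 11.4 months for single-agent pembrolizumab. Assume a constant hazard and take day 63 as 63/30.44 = 2.07 months.

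- From the median: 1 − exp(−(ln 2/11.4) × 2.07) = 11.8%, or 3.5 of 30.
- From the 6-month figure: 1 − 0.66^(2.07/6) = 13.4%, or 4.0 of 30.

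The 12-week life-expectancy criterion (3.2.6) may lower this.

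**5. Patients of unknown 6-month status.** If k unknowns count as failures, power is P(Bin(30 − k, 0.39) ≥ 10): 75.2%, 70.5% or 65.3% for k = 1, 2 or 3. The exact level falls to 4.9%, 3.9% or 3.0%. The alternative is a Kaplan-Meier 6-month estimate with its one-sided 90% lower bound compared with 20%. In simulation (exponential times, non-informative dropout of 10% or 20% by 6 months) this gave type I error of about 0.08-0.09 and power of about 0.78-0.81.

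**6. The week-27 scan.** Scans every 9 weeks fall at weeks 18 and 27. Week 27 is day 27 × 7 = 189, and 6 months is day 182.6. With ±5 days (Section 9 note 6, 10.1, 10.2.1, 10.3) the scan falls on days 184-194, always after 6 months. With ±7 days (4.6.2, 4.9.2) it falls on days 182-196. Section 10.3 dates confirmed progression at the first scan showing it. By date, then, progression first seen at week 27 is almost always after 6 months.

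Counting it as a 6-month failure is therefore a different endpoint. Suppose 39% are progression-free through week 18, with constant hazard and progression seen only at scans. The rate through week 27 is 0.39^(27/18) = 24.4%, and the power of the 10-of-30 rule is P(Bin(30, 0.244) ≥ 10) = 17% instead of 79%.

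**The case against.** The best reply is that the primary test is already in the plan. Section 12.1 gives the null, the binomial basis and the level for the primary endpoint, and the cutoff of 10 follows mechanically. That stands: a reader might infer that no test of the primary endpoint is planned, and 12.1 does not support that. What remains is that 12.2.1, the section that says how the primary endpoint is analysed, names a different quantity and gives no rule for unknown status.

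A second reply is that the type I error inflation appears only if the cutoff is re-derived for the smaller subset. That also stands. The plan states neither a cutoff nor a re-derivation rule, so both columns of the table are open. Nor should 12.3-12.7% be read as a doubling of 6.1%. The plan's limit is 10%, so the excess is 2.3-2.7 points.

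On censoring, a reader might infer that patients who switch therapy without documented progression would be counted as successes. No passage says so: 12.2.1 says censored. The sentence on last date known alive sits in the overall survival item, several sections end disease follow-up at new therapy, and the discontinuation scan (Section 9 note 9) limits the problem. The most natural reading of last follow-up for PFS is disease follow-up. The wording is unclear, but it does not prescribe a wrong rule.

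None of these replies removes the conflict between 12.2.1 and Table 8. The safety heading over 12.2.1 does not resolve it either, because the paragraph after the intent-to-treat sentence defines the primary endpoint.

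**Conclusion.** The point holds, and should be fixed before analysis, on two counts. The primary analysis in 12.2.1 does not make the decision specified in 12.1. The PFS population also differs between 12.2.1 and Table 8, in a way that can reverse that decision (9/30, p=0.129, against 9/28, p=0.090).

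The long-run size is modest and conditional. Type I error is 12.3-12.7% against a 10% limit if 2 to 5 early failures are dropped and the cutoff is re-derived. There is no inflation for one dropped patient or with the cutoff held at 10. The number dropped is assumed; it rests on a constant hazard and on early deaths missing the scan.

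Censoring is a secondary ambiguity. The design calculation itself is sound.

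**What to change.** 1. **Table 8.** Change the PFS subset to the intent-to-treat population of 12.2.1, and define that as all patients who start treatment, since PFS runs from first dose.
2. **Section 12.2.1.** State the primary analysis as the 12.1 test: exact one-sided 10% binomial test of 20%, reject at 10 or more of 30 (exact level 6.1%, power 79.3% at 39%), with the cutoff re-derived if n is not 30. Keep the Kaplan-Meier median as supportive. If any patient is censored before 6 months, report the Kaplan-Meier 6-month estimate with a one-sided 90% lower bound against 20%, and count unknowns as failures in a sensitivity analysis.
3. **Censoring.** Censor PFS at the last adequate tumour assessment, and limit the last-known-alive rule in 12.3 to overall survival.
4. **Scan timing.** Reconcile the ±5 and ±7 day windows. State in advance how progression first seen at the week-27 scan counts towards 6-month status, with the effect on power.

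Items 1 to 3 are text changes with no added visits. The sensitivity analysis has power of 75.2%, 70.5% or 65.3% with 1, 2 or 3 unknowns. The Kaplan-Meier alternative keeps power near 0.78-0.81 only if dropout is non-informative. Item 4 is not merely wording. Counting week-27 progression as failure would change the endpoint and, on the assumptions above, cut power from 79% to 17%. The documents do not show whether the 20% benchmark was measured that way.

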### 12.3. Secondary Analyses

Secondary efficacy analysis will be conducted for the efficacy evaluable population. Secondary endpoints and analyses are as follows:

To evaluate response rate (RR). Response will be determined by RECIST v1.1 for solid tumors. The 95% exact CI for the RR will be estimated using the Clopper-Pearson method. For objective responders, the duration of response is the time from the first objective response contributing to an objective response, to the first objective response of PD (by RECIST v1.1) occurring after the first objective response contributing to the objective response.

To evaluate overall survival (OS). Time-to-event data will be analyzed by the Kaplan-Meier method, treating subjects with no observed death or progression as censored at their last date known to be alive. For the OS analysis, the nonparametric Kaplan-Meier method will be used to estimate the survival time distribution and the median survival.

To assess the safety and tolerability of epacadostat in combination with pembrolizumab. AEs will be coded by the MedDRA, and incidences will be tabulated by preferred term and system organ class for all events, related events, and events  $\geq$  Grade 3. Severity of AEs will be based on the CTCAE v5 scale as indicated. Quantitative safety variables and their changes from baseline (laboratory, vital signs) will be summarized with descriptive statistics. Clinically significant abnormal values will be flagged and tabulated based on predefined criteria. Exposure will be analyzed by describing dose intensity, which is defined as the dose-received divided by the dose planned over a given time interval. This will be done by cycle as well as overall cycles received for epacadostat and pembrolizumab. For each cycle, incidences of dose reductions and cycle

delays will also be tabulated, by reason for the reduction or delay. The percentage of subjects with any delay and/or reduction will also be calculated.

Clinical Laboratory Tests. The clinical laboratory data will be analyzed using summary statistics (e.g., means and frequencies), and no formal statistical comparisons among the treatments are planned. In addition, distributions of key laboratory parameters (including hemoglobin, neutrophils, and platelets) will be plotted over time; these values will also be classified into CTCAE toxicity grades and tabulated. Descriptive statistics and mean change from baseline will be determined for vital signs at each assessment time. Vital sign results will be reviewed for clinically notable abnormalities.

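### Section 12.3 and Table 8 give overall survival conflicting analysis populations, and the OS censoring sentence does not fit the OS definition

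*Combined protocol and SAP*

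**What the plan says.** OS and response rate are secondary objectives (Section 1.2). The plan describes their populations and the OS event in several places.

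- **Section 12.3, opening sentence:** "Secondary efficacy analysis will be conducted for the efficacy evaluable population". RR and OS follow, with no exception for OS. The term is not defined anywhere in the document.
- **Table 8, OS column:** the relevant subset is "All enrolled patients" and the endpoint is "Time from first treatment until the day of death due to any cause". The measurement method shown for OS is CT or MRI every 9 weeks.
- **Table 8, PFS and RR columns:** the relevant subset is "Patients who receive baseline imaging and at least first follow-up imaging at 9 weeks". This is the only scan-based set the document describes.
- **Section 12.3, OS item:** time-to-event data are analysed by Kaplan-Meier, "treating subjects with no observed death or progression as censored at their last date known to be alive". The next sentence says that Kaplan-Meier will be used for OS and its median. No censoring rule specific to OS is given.
- **Section 12.2.1:** refers to an intent-to-treat population, under a safety heading and just before the primary endpoint text, without saying which endpoints it covers.

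**The concern.** There are two separate problems with OS and a related one with RR.

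**Population.** An analyst who follows Section 12.3 and one who follows Table 8 can produce different OS curves from the same data, and nothing says which statement takes precedence. If the evaluable set is taken to be the 9-week-scan set, a patient must survive to about week 9 to be counted, yet time is measured from first treatment. That is immortal time, and it favours the treatment.

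**Censoring.** The sentence under OS covers patients with neither death nor progression. A patient who has progressed but is alive falls outside it and has no stated rule. This conflicts with Table 8's OS definition, in which only death counts. It is a different conflict from the one over population.

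**RR.** Under Table 8's subset, patients who die or drop out before the first follow-up scan leave the denominator, although they are non-responders.

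At stake is the reported value of two secondary efficacy endpoints, and whether the rule producing them is fixed before the data are seen.

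**Working it through.** **The plan's own figure.** The documents give no power or precision figure for OS. The one design figure is for 6-month PFS: 30 patients, 20% against 39%, one-sided 10%, 80% power (Section 12.1). Exact binomial with 10 or more successes in 30 gives type I error 0.061 and power 0.793, which agrees with the stated 80%. A cut-off of 9 gives type I error 0.129, above 10%. OS has no test, so the OS rule does not enter this calculation.

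**Inputs for OS.** N = 30 ("We will enroll 30 patients over 18 months and follow patients for at least 6 months"). Section 2.1 gives, for the single-agent pembrolizumab gastric cohort, 6-month OS 66%, median OS 11.4 months, 6-month PFS 26% and median PFS 1.9 months. It also gives a median OS of 3 to 5 months for second-line trials. The 9-week scan is at 63/30.4375 = 2.07 months. Assumptions: exponential survival, and every death before week 9 excluded.

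**Formulas.** With hazard λ:
- fraction dead before week 9 = 1 − exp(−2.07λ)
- 6-month OS in the scan subset = S(6)/S(2.07)
- median in the scan subset, measured from first treatment = true median + 2.07 months

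**66% at 6 months.** λ = −ln(0.66)/6 = 0.0693 per month. S(2.07) = 0.866, so 13.4% (4.0 of 30) die before week 9. Subset 6-month OS = 0.66/0.866 = 0.762. The implied median moves from 10.0 to 12.1 months.

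**Median 11.4 months.** 11.8% (3.5 of 30) die before week 9. The subset median is 11.4 + 2.07 = 13.5 months.

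**Scan window.** Moving the scan by 7 days either way (1.84 to 2.30 months) changes the 76% to between 75% and 77%, and the 13.5 months to between 13.2 and 13.7.

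**Without the exponential form.** If 66% of 30 (19.8 patients) are alive at 6 months and k early deaths are excluded, the subset shows 19.8/(30 − k):

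| k excluded | 6-month OS |
|---|---|
| 0 | 66.0% |
| 1 | 68.3% |
| 2 | 70.7% |
| 4 | 76.2% |

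**Extreme case.** Medians of 3 to 5 months would mean 38% to 25% dead before week 9, 6-month OS of 40% to 58% instead of 25% to 44%, and medians of 5.1 to 7.1 months.

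**Censoring sentence.** Take the three possible states in turn. Dead: an event. Alive without progression: censored when last known alive. Alive with progression: no rule. If the third group were counted as events, the curve would be a PFS curve. In the cited cohort that means 26% instead of 66% at 6 months, and a median of 1.9 instead of 11.4 months. This acts in the opposite direction to the population effect.

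**RR illustration.** With 6 responders and 4 patients lacking the 9-week scan (the early-death count above), RR is 6/30 = 20% in all treated patients and 6/26 = 23% in the scan subset.

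**The case against.** The strongest reply is that the evaluable population is undefined, and that the one table describing a scan-based set assigns OS to a different one. Under a definition such as having received at least one dose, few or no early deaths would be lost. This stands. A reader might infer that OS will necessarily be overstated, but the documents do not support that. They support a contradiction, with upward bias under one plausible reading.

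The censoring sentence may be general wording for PFS and OS together, since OS is named only in the sentence after it. Table 8 makes death the OS event, and Section 4.6.3 continues survival calls every 12 weeks after progression. So the inference that the plan intends progression to end OS is not supported either. What remains is that the sentence is printed under OS and no other OS censoring rule exists.

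The 3 to 5 month medians are a stretch. They come from second-line trials outside the pembrolizumab cohort, and eligibility requires life expectancy of at least 12 weeks and ECOG 0 or 1 (Section 3.2). They mark an extreme. The cohort's two OS figures also do not fit a single exponential, because 66% at 6 months implies a median of 10.0 months, not 11.4. The results are illustrations.

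On RR, Section 12.3 and Table 8 are compatible, so there is no contradiction. The point is the choice of denominator.

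Finally, OS has no test or threshold, and Section 12.3 plans no comparison with historical survival. That limits the severity.

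**Conclusion.** The population conflict is certain as text, and so is the mismatch between the censoring sentence and the OS definition. The size and direction of any bias are conditional. If the evaluable set is the 9-week-scan set, survival is roughly exponential and the background figures apply, 6-month OS is inflated by about 10 percentage points (66% to 76%) and the median by about 2.1 months (11.4 to 13.5). Patients who stop before the scan without dying would also be excluded; their effect is not in these figures. Counting progression as an event would understate OS. The two defects pull in opposite directions, so the net direction is undetermined. The RR effect is about 3 points in the example.

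Changing the OS and RR rules leaves the primary test, N = 30 and the power as they are. Severity is moderate: these are untested secondary endpoints, but two stated rules conflict and the repair is simple.

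**What to change.** In Section 12.3:

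1. Analyse OS in all enrolled patients, as Table 8 says. In practice this means those who start treatment, because the OS clock starts at first treatment; report the number of any enrolled patients never treated.
2. Make death from any cause the only OS event. Censor everyone not known to have died at the date last known alive, whether or not they have progressed.
3. Define the efficacy evaluable population and keep it for supportive analyses.
4. Report RR in all treated patients, counting those without a post-baseline scan as non-responders, and align Table 8's RR subset.

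The cost is a few sentences, settled before the data are examined. No new data are needed, because survival follow-up by telephone already continues after progression (Section 4.6.3). The OS and RR estimates may come out slightly less favourable than under the scan-based set.
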